8.2. Safety Analyses

8.2.1. Overview of Planned Analyses

The safety analyses will be based on the Intent-To-Treat (ITT) population, unless otherwise specified in [Appendix 13: List of Data Displays](#). The safety displays to be created as part of the RAP include all the required and relevant displays identified as per the RAP Core Safety Reporting Template Version 1.0.

Table 6 provides an overview of the planned analyses, with further details of data displays being presented in [Appendix 13: List of Data Displays](#).

Adverse events will be coded using the latest version of the Medical Dictionary for Regulatory Activities (MedDRA).

Table 6 Overview of Planned Adverse Event Analyses

Endpoint / Parameter/ Display Type	Absolute		
	Summary		Individual
	T	F	L
Exposure			
Number of treatments administered and time on-treatment	Y		Y
Adverse Events (AEs)			
Overview of Adverse Events	Y		
AEs by SOC and Maximum Intensity	Y		Y
Common Adverse Events by Overall Frequency ^[1]	Y		
All Drug-Related AEs by SOC and Maximum Intensity	Y		
AEs on the Day of Dosing	Y		
AEs by the Age Group (<18 year, ≥18 years)	Y		
AEs by Highest Antidrug Antibody Result At Any Time Post Baseline	Y		
Number of subjects & occurrences of common ^[1] non-serious AEs by SOC and PT	Y		
Subject Numbers for Individual AEs			Y
Relationship between AE SOCs, PT & verbatim text			Y
Serious and Other Significant AEs			
Fatal Serious AEs	Y		Y
Non-Fatal Serious AEs	Y		Y
Serious AEs by SOC	Y		
Reasons for Considering as a Serious AE			Y
Drug-Related Serious AEs by SOC and Maximum Intensity	Y		
AEs Leading to Withdrawal from Study / Permanent Discontinuation of Study Treatment by Overall Frequency	Y		Y
Number of Subjects and Occurrences of Serious, Drug-Related Serious, Fatal Serious, and Drug-Related Fatal Serious AEs	Y		
Adverse Events of Special Interest (AESI) (On-Treatment) ^[2]			
Anaphylaxis	Y		Y
Systemic Allergic/Hypersensitivity and Non-allergic Reactions	Y		Y

Endpoint / Parameter/ Display Type	Absolute		
	Summary		Individual
	T	F	L
Systemic Allergic/Hypersensitivity Reactions	Y		
Systemic Non-allergic Reactions	Y		
Local Injection Site Reactions	Y		Y
Opportunistic Infections	Y		Y
Malignancies	Y		Y
Serious Cardiac, Vascular and Thromboembolic Events	Y		Y
Serious Ischemic Events	Y		Y
Cardiovascular Events			
All Cardiovascular Events	Y		Y

NOTES:

- T = Table, F = Figures, L = Listings, Y = Display generated, SOC=System Organ Class, PT=Preferred Term.
- Summary = Represents TF related to any summaries (i.e. descriptive statistics) of the observed raw data.
- Individual = Represents FL related to any displays of individual subject observed raw data.

[1] Common AEs will be defined as AEs with frequency $\geq 3\%$ (prior to rounding to nearest percent).

[2] On-treatment Summary Profiles of each type of AE of Special Interest will also be presented.

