## 4. STUDY DESIGN

### 4.1. Overall Design

The study will be a multi-centre, open-label single arm trial. Patients with severe eosinophilic asthma who are receiving omalizumab, but are not optimally controlled will be eligible to participate and will be identified through the ACQ-5 with a screening (Visit 1) and baseline (Visit 2) score of  $\geq 1.5$  and a history of  $\geq 2$  exacerbations in the past 12 months. For those subjects receiving omalizumab for  $\geq 8$  months, at least 1 exacerbation must be while on omalizumab treatment.

Subjects meeting all the inclusion/exclusion criteria at screening Visit 1, will enter a run-in period for a minimum of one week and up to 4 weeks to assess subjects' eligibility and compliance with study-related procedures.

[figure not shown]
Subjects will remain on their current maintenance therapy throughout the run-in period, including omalizumab. At Visit 2 subjects will discontinue omalizumab treatment and be switched to mepolizumab 100 mg SC every 4 weeks. Except for omalizumab, subjects will remain on their current maintenance therapy throughout the open-label treatment period.

Every subject, including those who withdraw early from the study, will be asked to return for an Exit Visit approximately 4 weeks after their last dose of study treatment.

An Exit interview will be conducted during the Exit Visit or early withdrawal Visit in a subset of participating sites and in a subset of patient who consent to participate.

The investigator is responsible for ensuring that consideration has been given to the post-study care of the patient's medical condition. At the end of the study, subjects may be prescribed appropriate alternative asthma therapy if needed and as determined by the study Investigator.

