## 5.5. Withdrawal/Stopping Criteria

### 5.5.1. Withdrawal from Study Treatment

Subjects may be withdrawn from study treatment at any time by the Investigator if it is considered to be detrimental for them to continue in the study. Reasons for withdrawal from study treatment can include: an adverse event (including abnormal liver function test or abnormal laboratory results), clinically significant abnormality identified on ECG, lost to follow-up, protocol violation, lack of efficacy, sponsor terminated study, non-compliance, continued in error, pregnancy, or for any other reason.

Subjects who have permanently withdrawn mepolizumab study treatment are not required to withdraw from the study. Every effort should be made to complete all remaining protocol specified visits even if they have discontinued mepolizumab treatment provided there are no safety concerns with doing so.

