Administer mepolizumab. Contact RAMOS NG to register dispensing visit.			X	X	X	X	X	X	X	X		
Albuterol/salbutamol dispensed (as needed)		X	X	X	X	X	X	X	X	X		
Collect dispensed albuterol/salbutamol			X	X	X	X	X	X	X	X	X	
eCRF/ paper diary/worksheet												
Complete eCRF	X	X	X	X	X	X	X	X	X	X	X	
Dispense paper diary/worksheet	X	X	X	X	X	X	X	X	X	X		
Collect/review paper diary/worksheet		X	X	X	X	X	X	X	X	X	X	
1. Pre-screen Visit 0 must be completed prior to Visit 1 (Screening). It can be completed on the same day as Visit 1 or at up to 2 weeks prior to Visit 1. 2. Subjects will be assigned a subject number at the time ICF signed. The ICF must be signed before any study procedures including medication wash out period(s). 3. Exit Visit may be completed 3 to 5 weeks post last dose. 4. Therapy history to include a detailed review of prior biologics received for treatment of asthma, including omalizumab dose and regimen and prior investigational therapies e.g anti-IL5 or anti-IL13 preparations. 5. All study efficacy, safety and all patient reported questionnaires must be completed prior any study procedure. 6. Spirometry to include pre- and post bronchodilator FEV1 from V2. 7. Exit interview will be conducted only in a subset of sites and in a subset of subjects who choose to participate in the Exit interview. Subjects must be consented prior to interview 8. Parasitic screening is only required in countries with high-risk or for subjects who have visited high-risk countries in the past 6 months. Sites should use local laboratories. 9. Pharmacogenetic sample may be drawn at Visit 2 or any visit after. 10. Pregnancy test, U= urine 11. Hepatitis B Surface Antigen and Hepatitis C antibody. (if hepatitis C antibody is positive, hepatitis C will be confirmed by PCR).												

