#### 7.4.1.1. Time period and Frequency for collecting AE and SAE information

- Any SAEs assessed as related to study participation (e.g., protocol-mandated procedures, invasive tests, or change in existing therapy) or related to a GSK product will be recorded from the time a subject consents to participate in the study up to and including any follow-up contact.
- AEs will be collected from the start of Study Treatment until Exit Visit at the time-points specified in the Time and Events Table (Section 7.1).
- Medical occurrences that begin prior to the start of study treatment but after obtaining informed consent may be recorded on the Medical History/Current Medical Conditions section of the CRF.
- All SAEs will be recorded and reported to GSK within 24 hours, as indicated in [Appendix 7](#)
- Investigators are not obligated to actively seek AEs or SAEs in former study subjects. However, if the investigator learns of any SAE, including a death, at any time after a subject has been discharged from the study, and he/she considers the event reasonably related to the study treatment or study participation, the investigator must promptly notify GSK.

NOTE: The method of recording, evaluating and assessing causality of AEs and SAEs plus procedures for completing and transmitting SAE reports to GSK are provided in Section 12.7, [Appendix 7](#).

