10.4.3. Treatment Phases (Adverse Events)

Adverse events will be classified according to time of occurrence relative to the first and last date of the study treatment.

Treatment Phase	Definition
Pre-Treatment	AE Onset Date & time < First dose of mepolizumab If mepolizumab treatment is never started then all AEs will be classified as pre-treatment.
On- Treatment	First dose of mepolizumab ≤ AE Onset Date & time ≤ Last dose of mepolizumab + 28 days If an AE start date is missing or partial then the AE will be considered on-treatment unless there is evidence to the contrary (e.g. month/year of onset date is present and is earlier than the month/year of First dose of mepolizumab).
Post-treatment	AE Onset Date & time > Last dose of mepolizumab + 28 days

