3.19	ITT	AE1	Summary of Serious Adverse Events by System Organ Class (On-Treatment)		SAC
3.20	ITT	AE1	Summary of Serious Adverse Events by System Organ Class (Post-Treatment)		SAC
3.21	ITT	AE1	Summary of Drug-Related Fatal Serious Adverse Events by System Organ Class		SAC
3.22	ITT	AE1	Summary of Drug-Related Serious Adverse Events by System Organ Class and Maximum Intensity	Add a Total column across all severities	SAC

Safety : Tables					
No.	Population	IDSL / TST ID / Example Shell	Title	Programming Notes	Deliverable
3.23	ITT	AE3	Summary of Adverse Events Leading to Permanent Discontinuation of Study Treatment or Withdrawal from Study by Overall Frequency		SAC
3.24	ITT	AE16	Summary of Number of Subjects and Occurrences of Serious Adverse Events by System Organ Class and Preferred Term		SAC
Adverse Events of Special Interest					
3.25	ITT	AE1	Summary of AEs meeting Anaphylaxis Criteria (On-Treatment)	Present by Anaphylactic Criterion 1, 2 and 3 rather than SOC as shown in AE1	SAC
3.26	ITT	SHELL	Summary Profile of AEs meeting Anaphylaxis Criteria (On-Treatment)		SAC
3.27	ITT	AE1	Summary of AEs Defined by the Investigator as being Systemic (non-allergic or allergic/hypersensitivity) Reactions (On-Treatment)		SAC
3.28	ITT	SHELL	Summary Profile of Systemic (non-allergic or allergic/hypersensitivity) Reactions (On-Treatment)		SAC
3.29	ITT	SHELL	Summary Profile of Systemic Allergic Reactions (On-Treatment)		SAC
3.30	ITT	SHELL	Summary Profile of Systemic Non-Allergic Reactions (On-Treatment)		SAC
3.31	ITT	AE1	Summary of AEs Defined by the Investigator as being Local Injection Site Reactions (On-Treatment)		SAC
3.32	ITT	AE1	Summary of AEs Defined by the Investigator as being Local Injection Site Reactions by Relation to IP (On-Treatment)		SAC
3.33	ITT	SHELL	Summary Profile of Local Injection Site Reactions (On-Treatment)		SAC

Safety : Tables					
No.	Population	IDSL / TST ID / Example Shell	Title	Programming Notes	Deliverable
3.34	ITT	AE3	Summary of Opportunistic Infections (On-Treatment)		SAC
3.35	ITT	SHELL	Summary Profile of Opportunistic Infections (On-Treatment)		SAC
3.36	ITT	AE3	Summary of Malignancies (On-Treatment)		SAC
3.37	ITT	SHELL	Summary Profile of Malignancies (On-Treatment)		SAC
3.38	ITT	AE1	Summary of Serious Cardiac, Vascular and Thromboembolic Adverse Events (On-Treatment)		SAC
3.39	ITT	SHELL	Summary Profile of Serious Cardiac, Vascular and Thromboembolic Adverse Events (On-Treatment)		SAC

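### The type-specific AESI tables stop at last dose + 28 days and have no post-treatment counterpart, so later events that the trial collects are missing from the AESI subject counts

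*SAP*

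**What the plan says.** **Analysis window.** SAP 8.2.1 (Table 6) heads the AESI block "Adverse Events of Special Interest (AESI) (On-Treatment", and the table's second note makes the AESI profiles on-treatment too. SAP 10.4.3 defines the on-treatment phase for adverse events as "First dose of mepolizumab ≤ AE Onset Date & time ≤ Last dose of mepolizumab + 28 days"; anything with "AE Onset Date & time > Last dose of mepolizumab + 28 days" is post-treatment. In SAP 10.13.1.5, Tables 3.25 to 3.41 all have the restriction in their titles, for example "Summary of Malignancies (On-Treatment" for Table 3.36. No post-treatment or any-time version of these 17 displays is listed. Table 3.42, which combines serious AEs and AESIs, has no phase in its title.

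**Collection period.** Protocol 7.4.1.1 says "AEs will be collected from the start of Study Treatment until Exit Visit". Footnote 3 of the Time and Events Table (Protocol 7.1) says "Exit Visit may be completed 3 to 5 weeks post last dose". For subjects who stop dosing, Protocol 5.5.1 says "Every effort should be made to complete all remaining protocol specified visits even if they have discontinued mepolizumab treatment", unless safety concerns prevent it. Protocol 4.1 says that every subject, including those who leave the study early, "will be asked to return for an Exit Visit approximately 4 weeks after their last dose of study treatment".

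**Other displays.** All AEs have post-treatment tables (3.5, 3.6), as do non-fatal SAEs (3.17) and all SAEs (3.20). Table 3.43 (investigator-reported cardiovascular events) and AESI Listings 19 to 26 have no phase label.

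**The concern.** Infection, malignancy and cardiovascular effects are among the potential risks that the sponsor names in Protocol Table 3. SAP 8.2.2 promises the number and percentage of subjects with each type of AESI and sets no time limit in that text. The display list then narrows the counts to 28 days after the last dose, although all AEs and SAEs are also shown for the later period.

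A dosing-interval window suits injection-site and acute systemic reactions. It suits malignancies, opportunistic infections and ischaemic events less well, because their onset need not follow a dose closely. The subjects with the longest uncounted time are those who stopped treatment early and stayed, which may include some who stopped because of harm. With 120 treated subjects, one uncounted subject moves an AESI incidence by 1/120 = 0.83 percentage points.

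The SAP also treats the same days differently elsewhere. For completers, exacerbations (10.4.1) and visit-based efficacy data (10.4.2) are on-treatment up to the Exit Visit. The primary efficacy analysis (7.1.2) keeps data collected after treatment discontinuation.

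**Working it through.** The plan states no figure for AESI follow-up, so there is nothing to reproduce. The check is date arithmetic, counting days from the first dose (day 0) and assuming doses on the nominal schedule.

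**Inputs**
- Doses every 4 weeks, eight in all, the last at Week 28 = day 196 (Protocol 4.2).
- AE on-treatment phase ends at last dose + 28 days (SAP 10.4.3).
- Exit Visit 21 to 35 days after the last dose (Protocol 7.1, footnote 3).
- Week 32 = day 224; 120 treated subjects (Protocol 4.3).

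**Completers**
- On-treatment phase ends on day 196 + 28 = 224.
- Exit Visit falls between day 196 + 21 = 217 and day 196 + 35 = 231.
- Largest gap: 231 − 224 = 7 days, or 7/231 = 3.0% of follow-up.
- If Exit Visits were spread evenly over the 15 permitted days, the mean gap would be (1 + 2 + … + 7)/15 = 28/15 = 1.9 days.

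**Subjects who withdraw from the study**
- Their Exit Visit is also about 4 weeks after the last dose, so the gap is again about 7 days at most.

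**Subjects who stop mepolizumab after k doses and stay to Week 32**
- Last dose on day 28(k − 1); on-treatment phase ends on day 28k.
- Gap = 224 − 28k days.

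| Doses received | 1 | 2 | 3 | 4 | 5 | 6 | 7 |
|---|---|---|---|---|---|---|---|
| Gap (days) | 196 | 168 | 140 | 112 | 84 | 56 | 28 |
| Gap (weeks) | 28 | 24 | 20 | 16 | 12 | 8 | 4 |

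If the last visit falls 7 days late, the range becomes 35 to 203 days.

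**Share of planned follow-up**
- Planned subject-weeks: 120 × 32 = 3,840.
- Assumption, because the documents give no rate: 5% to 15% of 120, that is 6 to 18 subjects, stop and stay.
- Lowest: 6 × 4 / 3,840 = 0.6%.
- With the mean gap of 16 weeks: 6 × 16 / 3,840 = 2.5% to 18 × 16 / 3,840 = 7.5%.
- Highest: 18 × 28 / 3,840 = 13.1%.

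**Can the counts be rebuilt from other tables?** SAP 8.2.2 identifies these four AESI types from lists of preferred terms, whereas the post-treatment tables are arranged by system organ class. Protocol Table 3 itself notes that thrombotic events such as stroke sit in the nervous system class. The number of subjects with, say, any serious CVT event therefore cannot readily be read from tables by class: the relevant terms are spread over several classes, and a subject may appear in more than one.

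**The case against.** The restriction is openly labelled, prespecified and consistent between Table 6 and the display titles, and the window equals the dosing interval. Late events have other places to appear. SAP 8.2.2 says that infections, neoplasms and cardiac disorders are also reported in the standard AE tables, and those tables have post-treatment versions. Serious CVT and serious ischaemic events are SAEs by definition, so late ones fall in Table 3.20. Malignancies generally should too, since Protocol Appendix 7 gives malignant cancer as an example of a serious event. In a single-arm study of about 120 subjects, individual cases can be traced through the listings. The Program Safety Analysis Plan, to which the SAP refers for identifying AESI terms, is not available here and might say more about windows.

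Most of this stands, and it rules out several stronger readings:
- A reader might infer that every AESI summary is restricted. Table 3.42 is not labelled, so its phase is simply unstated.
- A reader might infer that late events disappear from the report. They do not.
- A reader might infer that anything found at an Exit Visit on days 29 to 35 is excluded. Phase follows onset date, so an event found on day 33 with onset by day 28 is counted. Missing or partial start dates default to on-treatment unless there is contrary evidence.
- A reader might note that 7 of the 15 permitted Exit Visit days (47%) fall after the cut-off. That is a share of visit days, not of events or follow-up.
- A reader might take the 15% in Protocol 9.2.1 as an upper bound on those who stop and stay. It refers to subjects who leave the study and lack Week 32 data, a different group. Some who stop for harm also belong there: subjects meeting the QTc criteria are withdrawn from the study (Protocol 5.5.4).

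The objection does not supply AESI subject counts for the period after day 28. Listings show cases, and tables by system organ class do not give the number of subjects per AESI type.

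**Conclusion.** The point holds for Tables 3.25 to 3.41: they omit collected events with onset more than 28 days after the last dose, and no companion table counts those events by AESI type. It is a reporting gap. No data are lost, and no endpoint or hypothesis test is affected.

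For completers and study withdrawers the gap is small. It is material only for subjects who stop treatment and stay, and its total size rests on an assumed proportion of such subjects.

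It also rests on when their Exit Visit takes place. Protocol 4.1 and 7.1 tie that visit to the last dose. Protocol 5.5.1 asks these subjects to complete the remaining visits, and 5.6 lets a subject complete the study without completing treatment. If AE collection for this group ended at an Exit Visit about 4 weeks after the last dose, the long gap would shrink to about a week. The change is still worth making, because it is cheap and could alter the reported incidence of rare events.

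**What to change.** - In SAP Table 6 and Appendix 13, report opportunistic infections, malignancies, serious CVT events and serious ischaemic events (Tables 3.34 to 3.41) for the whole collected period after the first dose, with on-treatment and post-treatment shown separately.
- State the phase of Table 3.42.
- The on-treatment limit can stay for injection-site and acute systemic reactions.
- Reconcile Protocol 4.1, 5.5.1, 5.6 and 7.1 on the Exit Visit timing, and hence the end of AE collection, for subjects who stop mepolizumab but remain in the study.

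**Cost.** Display wording, a phase split in eight existing tables, one label on Table 3.42 and a clarification of visit timing. The reporting change needs no new data. The drawback is that counts may look slightly less favourable and may include events after drug effect has waned; the phase split lets the reader see which those are.

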8.2.2. Adverse Events of Special Interest

Adverse events of special interest (AESIs) are adverse events associated with the identified and potential risks of mepolizumab. AESIs of anaphylaxis reactions, systemic reactions, and local injection site reactions are collected via targeted eCRF within the study. Events captured on the eCRF as systemic reactions will be further categorized as allergic/hypersensitivity reactions or non-allergic reactions. Events with preferred terms such as injection related reaction or administration related reaction will be considered non-allergic reactions. All remaining events will be considered allergic/hypersensitivity reactions.

AESIs of opportunistic infections, malignancies, serious CVT events and serious ischemic events will be identified from a list of relevant preferred terms maintained within a project level reference dataset created based on the MedDRA dictionary available at the time of database freeze for this study, further details of how relevant preferred terms are identified are given in the Program Safety Analysis Plan (PSAP).

Separate summary tables showing the number and percent of subjects with each type of AESI, broken down by preferred term will be created. Information will be reported as part of the standard AE tables for AESIs of infections, serious infections, neoplasms, cardiac disorders and serious cardiac disorders.

For each type of AESI a profile summary table will be produced containing information which would include, but not be limited to, the number of occurrences of the event, event characteristics, time to onset, intensity, outcome and action taken.

A listing of any subjects with systemic events identified by the investigators as meeting the criteria for anaphylaxis as outlined by the 2006 Joint National Institute of Allergy and Infectious Disease/Food Allergy and Anaphylaxis Network Second Symposium on

Anaphylaxis [Sampson, 2006] will be provided. Adverse events experienced on a day of dosing will be summarised and presented by SOC and preferred term.

A listing of all adverse events experienced by subjects who have had at least one investigator defined systemic reaction will be provided.

Cardiovascular events will be captured on targeted CV event pages of the CRF for the following AEs and SAEs:

- Myocardial infarction/unstable angina
- Congestive heart failure
- Arrhythmias
- Valvulopathy
- Pulmonary hypertension
- Cerebrovascular events/stroke and transient ischemic attack
- Peripheral arterial thromboembolism
- Deep venous thrombosis/pulmonary embolism
- Revascularization

8.2.3. Overview of Planned Clinical Laboratory Analyses

Safety analyses will be based on the Intent-To-Treat (ITT) population, unless otherwise specified in [Appendix 13: List of Data Displays](#). The safety displays to be created as part of the RAP include all the required and relevant displays identified as per the RAP Core Safety Reporting Template Version 1.0.

[Table 7](#) provides an overview of the planned analyses, with further details of data displays being presented in [Appendix 13: List of Data Displays](#).

Table 7 Overview of Planned Clinical Laboratory Analyses

Endpoint / Parameter/ Display Type	Absolute			Change from BL		
	Summary		Individual	Summary		Individual
	T	F	L	T	F	L
Chemistry						
Change from Baseline in Clinical Chemistry by Visit				Y		
Chemistry Results (Change from Baseline Relative to Normal Range)	Y			Y		
Hematology						
Change From Baseline in Haematology by Visit				Y		
Haematology Results (Change from Baseline Relative to Normal Range)	Y			Y		
Hepatobiliary (Liver)						
Liver Monitoring/Stopping Event Reporting			Y			
Chemistry Results for Subjects Meeting Liver			Y			

Endpoint / Parameter/ Display Type	Absolute			Change from BL		
	Summary		Individual	Summary		Individual
	T	F	L	T	F	L
Monitoring/Stopping Event Criteria						
Medical Conditions for Subjects with Liver Stopping Events			Y			
Alcohol Intake for Subjects with Liver Stopping Events			Y			
Hepatobiliary Laboratory Abnormalities	Y		Y			
Scatter Plot of Maximum Post-Baseline vs. Baseline for ALT		Y				
Scatter Plot of Maximum Post-Baseline ALT vs Maximum Post-Baseline Total Bilirubin		Y				
All Laboratory						
All Laboratory Data for Subjects with any Value of Potential Clinical Concern			Y			

NOTES:

- T = Table, F = Figures, L = Listings, Y = Yes display generated, PCI = Potential Clinical Importance
- Summary = Represents TFL related to any summaries (i.e. descriptive statistics) of the observed raw data.
- Individual = Represents FL related to any displays of individual subject observed raw data.

